Because of the relatively poor rate of success and the high frequency of adverse reactions to TMP-SMX and pentamidine, alternative regimens are being investigated. Pilot trials have reported success using pentamidine aerosol, trimetrexate with and without sulfadiazine, and difluoromethylornithine (30,31,32). The potential roles of these regimens in treating P. carinii pneumonia remain to be defined.

Prevention of P. carinii is also an area of active investigation. Fischl and colleagues (33) have reported that TMP-SMX given prophylactically to HIV-infected persons not only reduced the frequency of P. carinii pneumonia but also significantly prolonged life. Similarly, preliminary data from Leung and coworkers (34) and Feigal and associates (35) strongly suggest that aerosol pentamidine is effective in decreasing the incidence of P. carinii pneumonia in selected groups of patients with HIV infection. As with experimental therapies for P. carinii pneumonia, the role, general applicability, and impact of these preventive regimens have not yet been defined.

In addition to specific prophylaxis for P. carinii, the antiviral agent, azidothymidine (AZT), also decreases the incidence and severity of P. carinii pneumonia in selected groups of HIV-infected persons (36). It might be anticipated that more widespread use of AZT will in itself decrease the overall frequency of P. carinii pneumonia.

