to answer this question all HIV seropositive subjects (e.g., Groups A and B) will be included in the analysis. Possible predictor variables are HIV antibody status, stage of HIV infection, and HIV transmission category. Confounding variables are preventive treatment for infections, anti-HIV therapy, and immunosuppressive drugs. One of the principal outcome variables in this analysis will be presence or absence of P. carinii pneumonia. In order to calculate the prevalence of P. carinii pneumonia at, for example, 2 years into the study, a logistic regression model will be utilized which has the presence or absence of P. carinii pneumonia as the outcome variable and has the predictive and confounding variables as covariables. In this way, gross and adjusted odds ratios may be computed for the different subgroups of interest and the statistical equivalence of the magnitude of the gross or adjusted ratios may be assessed.

The second question in the primary objective concerns the association of various pulmonary diseases with subsequent morbidity and mortality. All seropositive subjects are to be part of this analysis and in this case P. carinii pneumonia will be one of the predictor variables. Confounding variables are transmission category, clinical and immunologic stage of HIV infection, and other coexisting diseases. One of the primary outcome variables for this analysis is mortality. In order to investigate the relationship of the presence or absence of P. carinii pneumonia on survival, a Cox regression model will be used in which mortality is the dependent variable and the presence or absence of P. carinii pneumonia is the predictive variable. The confounding variables above will appear as independent variables as well. In this analysis, comparisons will be made between the adjusted survival rates for those patients who developed P. carinii pneumonia versus those who do not over the course of the study.

Question 3 is, "What is the frequency with which multiple pulmonary diseases are present simultaneously and what are the common associations?" Again all HIV seropositive subjects will be used in this analysis and the major pulmonary diseases of interest will be P. carinii pneumonia, tuberculosis, mycobacterium avium complex infection, and cytomegalovirus infection. In order to discover associations which may exist among the different pulmonary diseases of interest, contingency

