Half-width 95% confidence interval for incidence of P. carinii pneumonia is 2% in Group A and 3% in Group B.

Question 2. What is the association of the following pulmonary diseases with subsequent morbidity and mortality: P. carinii pneumonia, tuberculosis, Mycobacterium avium complex infection, cytomegalovirus infection? Associations with subsequent morbidity and mortality will also be sought for less frequent processes including NIP, LIP, pyogenic bacterial infections, fungal infections and Kaposi's sarcoma involving the lungs. However, because of the infrequency of these processes, associations may be difficult to establish.

Groups studied

All HIV seropositive subjects

Predictive variables

Specific diseases as defined in Appendix 2

Confounding variables

HIV transmission category

Clinical and immunologic stage of HIV infection

Coexisting diseases

Diseases developing subsequently

Multiple pathogens present in the same patient

Outcome variables

Survival

Rate of change in pulmonary function

Days in hospital

Rate of weight loss

Rate of change in performance status

Evolution of chest film

Analysis

The analyses will be based on regression type models (linear, logistic, Cox regression) or multiple contingency table analysis models. Statistical measures studied will include differences in the rates (e.g., differences in the rates of specific abnormalities on chest films between those who had and those who did not have a specific pulmonary process) or means (e.g., days in hospital, rate of weight loss)

Question 3. What is the frequency with which multiple pulmonary diseases are present simultaneously and what are the common associations?

Groups studied

All HIV seropositive subjects

Predictive variables

Specific diseases (Appendix 2)

Confounding variables

HIV transmission category
Clinical and immunologic stage of HIV infection
Preventive therapy for infections

Outcome variables

Coexisting diseases

Analysis

The joint distributions of pulmonary diseases present at the same time in a patient will be analyzed using methods for categorical data. Significant associations among diseases will be described.

Question 4. What are the prevalence and incidence of specified symptoms, signs, radiographic findings, pulmonary function test abnormalities, laboratory findings, immunologic abnormalities and presence of indicators of HIV activity in patients with specific pulmonary diseases?

Groups studied

All HIV seropositive subjects

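### Both covariate lists for Question 2 omit antiviral and anti-pneumocystis preventive therapy, so the estimated association of PCP with death may be confounded, in a direction the protocol cannot settle

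*Protocol*

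**What the plan says.** Section 9 presents Question 2 as the second question of the primary objective. It specifies a Cox model with mortality as the dependent variable and presence or absence of PCP as the predictor. The covariates are named: "Confounding variables are transmission category, clinical and immunologic stage of HIV infection, and other coexisting diseases". It then says that "The confounding variables above will appear as independent variables as well", and that "comparisons will be made between the adjusted survival rates for those patients who developed P. carinii pneumonia versus those who do not".

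Appendix 1, Question 2, repeats transmission category, stage and coexisting diseases. It adds diseases that develop later and "Multiple pathogens present in the same patient". No therapy variable is in either list.

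Elsewhere the protocol does treat therapy as a confounder. For Question 1, where PCP is an outcome, Section 9 states: "Confounding variables are preventive treatment for infections, anti-HIV therapy, and immunosuppressive drugs". Appendix 1 lists antiviral and preventive therapy for Questions 5 to 8 and for Questions 12 to 14. Question 12 has mortality as its outcome.

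Section 3.3 reports that "TMP-SMX given prophylactically to HIV-infected persons not only reduced the frequency of P. carinii pneumonia but also significantly prolonged life". Of AZT it says that it "also decreases the incidence and severity of P. carinii pneumonia in selected groups of HIV-infected persons". It also cautions that "the role, general applicability, and impact of these preventive regimens have not yet been defined".

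**The concern.** Question 2 joins the outcome of Question 1 (PCP) to the outcome of Question 12 (death). The protocol regards therapy as a confounder for each of those separately, then leaves it out of the one model that relates them. Question 12 compares randomized groups, for which Section 9 itself says selection bias is much less of a worry. Question 2 compares subjects who do and do not develop PCP, with no randomization, so it depends more on adjustment.

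Section 6 acknowledges that therapy is not controlled by the study and may affect course and outcome. It also expects prophylaxis and AZT to be used more widely. Stage is in the model, but two subjects at the same stage can differ in therapy. An analyst who follows the text would report a PCP hazard ratio that may partly reflect who was treated, and a reader could not correct it afterwards.

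**Working it through.** The protocol gives no hazard ratio, power or precision for Question 2, so there is no figure to reproduce. The check has three parts.

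**1. Therapy in the confounder lists**

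| Question | Outcome | Antiviral | Preventive |
|---|---|---|---|
| 1 | specific lung diseases, including PCP | yes | yes |
| 2 | survival and morbidity after lung disease | no | no |
| 3 | coexisting diseases | no | yes |
| 5 to 8 | recurrent PCP; specific lung diseases | yes | yes |
| 12 to 14 | mortality, hospital days, performance status | yes | yes |

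**2. Direction of bias from leaving therapy out**

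For an omitted binary covariate, approximately:

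HR observed / HR true = (1 + p1(g − 1)) / (1 + p0(g − 1))

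Here p1 and p0 are the shares on therapy among subjects with and without PCP, and g is the hazard ratio of death for therapy apart from any effect through PCP. The formula ignores adjustment for stage.

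From the protocol: one-year PCP risk of 20% in Group B (Appendix 3). Assumed, because the protocol gives no values: uptake q of 20%, 50% or 80%; risk ratio r for PCP on therapy of 0.3, 0.5 or 0.7; g from 0.5 to 1.6.

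Worked cell with q = 0.5 and r = 0.3:
- PCP risk untreated = 0.20 / (0.5 × 0.3 + 0.5) = 0.308; treated = 0.3 × 0.308 = 0.092.
- p1 = 0.5 × 0.092 / 0.20 = 0.231; p0 = 0.5 × (1 − 0.092) / 0.80 = 0.567.
- g = 0.5: (1 − 0.5 × 0.231) / (1 − 0.5 × 0.567) = 1.23.
- g = 1.6: (1 + 0.6 × 0.231) / (1 + 0.6 × 0.567) = 0.85.

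Range over the nine combinations of q and r:

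| g | Bias factor | Meaning |
|---|---|---|
| 0.5 | 1.04 to 1.28 | therapy lowers death directly |
| 0.7 | 1.02 to 1.13 | as above, weaker |
| 0.9 | 1.01 to 1.04 | as above, slight |
| 1.0 | 1.00 | therapy acts on death only through PCP |
| 1.3 | 0.91 to 0.98 | therapy marks residual severity |
| 1.6 | 0.85 to 0.97 | as above, stronger |

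**3. Small Cox simulation**

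One seed, 8,000 subjects, time-updated PCP, true hazard ratio 3.0, half the subjects on therapy, hazard ratio 0.4 for PCP on therapy. All inputs are assumed.

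| Scenario | Without therapy | With therapy | With therapy and residual severity |
|---|---|---|---|
| Direct survival benefit (0.6), no channelling | 3.56 | 3.16 | 3.16 |
| Benefit only through PCP, no channelling | 3.15 | 3.17 | 3.17 |
| Direct benefit (0.6), sicker subjects treated more | 3.54 | 3.52 | 3.19 |
| Benefit only through PCP, sicker subjects treated more | 3.24 | 3.46 | 3.15 |

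With this seed even the fullest models return 3.15 to 3.19, so differences of that order from 3.0 carry no meaning. In the last row, omitting therapy gave a lower value than including it. Adding therapy alone moved the estimate away from 3.0, and adding severity as well brought it back. Therapy should therefore enter together with a severity measure taken at the same time.

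**The case against.** The best defence is that the lists are not closed. The introduction to Appendix 1 says they are not exhaustive, and Section 9 calls its detailed discussion illustrative and asks generally for adjustment where risk variables are unbalanced. This stands in part: nothing bars an analyst from adding therapy. But the Appendix 1 introduction names what it leaves implicit, namely comparisons with seronegative subjects and Clinical Center, and therapy is not among them. Section 9 says that its plans specify the confounders that enter the model, and it then names those for Question 2.

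A second objection concerns a stronger conclusion that a reader might draw: that PCP's link with death is overstated because both therapies lower PCP and prolong life. The documents do not support it, for three reasons.
- Prolonged life is reported only for TMP-SMX. For AZT and aerosol pentamidine Section 3.3 reports an effect on PCP and says nothing on survival.
- A survival gain obtained by preventing PCP runs through the exposure and is not confounding.
- If sicker subjects within a stage are treated more, the bias can reverse.

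Nor should an inflation range be quoted as the size of the error. Assuming no PCP effect on death, 30% PCP risk in non-users, uptake of 30 to 70%, a PCP risk ratio of 0.3 to 0.5 and a direct mortality ratio of 0.5 to 0.7 gives 1.05 to 1.27. Those inputs fix the direction in advance. They also assume that prophylaxis saves lives while the disease it prevents does not affect death.

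**Conclusion.** The omission is real and inconsistent with the protocol's own treatment of therapy in Questions 1, 5 to 8 and 12 to 14. It affects a non-randomized analysis within the primary objective, and the non-exhaustive wording does not repair it. The defensible conclusion is that the PCP-mortality estimate may be confounded: upward if therapy lowers mortality apart from PCP, nil if it works only through PCP, downward if it marks residual severity.

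No magnitude can be fixed, because the documents give neither uptake nor effect sizes. The factors of 1.01 to 1.28 (g of 0.5 to 0.9), 1.00, and 0.85 to 0.98 (g of 1.3 to 1.6) illustrate the three cases on assumed inputs and are not estimates for this study. The net direction is further obscured because Section 9 does not say that PCP enters as a time-dependent variable. Coding it as a fixed ever/never variable gave simulated hazard ratios of about 1.25 to 1.45 against a true 3.0. That is a separate matter, but it is another reason not to assert a direction.

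**What to change.** Add antiviral therapy and anti-pneumocystis preventive therapy to the Question 2 confounder lists in both Section 9 and Appendix 1, together with CD-4 count. For subjects who develop PCP, use the values in force before onset. For comparison subjects still free of PCP, use the values at the same follow-up time. State one updating rule and apply it to both groups, so that the covariates are not frozen in cases while they continue to update in the others. State also that therapy started because of the PCP episode is not adjusted for, since it is a consequence of the exposure.

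The variables are already planned for other questions, and Section 6, in discussing the screening comparison, asks for complete information on treatment. The cost is modest extra data handling to align the timing of the therapy and CD-4 values.

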7.1.3 Exclusion criteria

- 1) Younger than 18 years
- 2) Presence of a nonHIV-related process likely to affect survival
- 3) Judged unwilling or unable to cooperate with the study protocol
- 4) Use of immunosuppressive therapy (Table 4) within the past six months
- 5) Presence of an underlying disorder that makes future use of immunosuppressive therapy likely
- 6) Lung disease that may interfere with evaluations (Table 4)
- 7) Presence of pulmonary symptoms at baseline evaluation (Table 4) either new symptoms or a worsening of chronic symptoms
- 8) Current or previous AIDS-defining diseases (Subjects who meet all inclusion criteria and have no exclusion criteria yet have an AIDS-defining disease diagnosed on the initial evaluation will not be excluded.) (Table 4)
- 9) (Applies only to female partners of HIV infected men)
Receipt of blood or blood products or intravenous drug use in past 10 years

NonHIV-related processes likely to interfere with four-year survival include incurable neoplastic diseases, and severe cardiac, liver and renal disease. Such illnesses not only reduce the likelihood that the patient will complete the study, they also represent Table 4

Excluding Conditions and Therapies

1. Immunosuppressive therapy within previous 6 months.
Corticosteroids (systemic administration of >15 mg prednisone or equivalent amount of other preparation for >14 days)
Cytotoxic agents
Antimetabolites Cyclosporin
2. Lung diseases that may interfere with evaluation
Pneumonia, any cause, within 3 months
Invasive pulmonary fungal infection diagnosed within the past 12 months or continuing to receive treatment for such infection
Pulmonary mycobacterial disease diagnosed within the past 12 months or continuing to receive therapy for the disease
Diagnosed diffuse fiberoptic lung disease or sarcoidosis.
3. Respiratory symptoms
Unexplained cough that persists for more than five days
Unexplained breathlessness progressive over \geq five days or severe \geq one day
4. AIDS-defining diseases (MMWR 1987;37:45) (Appendix 10)
Items 1-12 Section I-B CDC definition
Items 1-12 Section II-A CDC definition
Items 1-7 Section II-B CDC definition

Note: Potential study subjects who at the time of initial evaluation are excluded because of any of the exclusions listed above (1-3), except fibrotic lung disease or sarcoidosis may be reevaluated for study entry after an appropriate time interval.

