All HIV seropositive subjects

Predictive variables

Absolute and relative numbers of CD4 cells. The CD4 cells will be grouped into 3 categories (>399, 200-399, <200) in some analyses.

Confounding variables

Antiviral therapy

Preventive therapy for HIV-related lung diseases

Outcome variables

Specific HIV-related lung diseases

Analysis

Regression models, appropriate when time dependant covariates are present, will be used to study this question.

Question 9. Do HIV infected persons who have not had lung diseases diagnosed have a greater incidence/prevalence of respiratory symptoms, pulmonary function abnormalities and unexplained radiographic findings than HIV seronegative subjects in the same transmission category?

Groups studied

All HIV seropositive and seronegative subjects

Predictive variables

HIV status

Transmission category

Confounding variables

Previous or current lung disease (recognized HIV-related or nonHIV- related)

Smoking

Outcome variables

Symptoms

Vital capacity, total lung capacity, forced expiratory volume in one second, diffusing capacity

Radiographic findings

Analysis

Analytic strategies involving regression models (linear and logistic) will be used

Question 10. Does pulmonary function deteriorate more rapidly in HIV infected persons who have not had lung diseases diagnosed compared with HIV seronegative subjects in the same transmission category?

Groups studied

All HIV seropositive and seronegative subjects

Predictive variables

HIV status

Transmission category

Confounding variables

Previous or current lung disease (recognized HIV-related or nonHIV-related)

Smoking

Outcome variables

Changes in vital capacity, total lung capacity, forced expiratory volume in one second, diffusing capacity over time

Analysis

Regression models will be used to address these questions.

Appropriate measures of decline (change) in lung function measurements will be used as outcome variables

Precision

Half-width 95% confidence intervals of DLCO for A versus C and B versus C are 2.0 for IV drug users and 1.3 for gays.

Question 11. How sensitive are symptoms for specific HIV-related lung diseases?

Groups studied

All HIV seropositive and seronegative subjects

Predictive variables

Fever (> 38R oral for > 5 days)

Cough (with or without sputum for > 5 days)

Shortness of breath (mild to moderate > 5 days, severe > 1 day)

Confounding variables

Preexisting lung disease

NonHIV-related lung diseases

Outcome variables

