The same tables may be used to judge the precision of the comparison between homosexual/bisexuals and IV drug users relative to the PCP as set forth in Question 6. Table 3.3 indicates that a difference of .04 at the end of one year of follow-up would be judged significant for the comparison of homosexual/bisexuals versus IV drug users.

Tables 3.4 through 3.6 are relevant in answering questions about the precision of comparisons in Question 10. Tables 3.4-3.6 deal with the precision of comparisons in DLCO. Groups A, B and C are of interest in these tables. A standard deviation of 2.5 is used for the DLCO calculations. According to Question 10, the primary comparisons of interest are Group A versus Group C and Group B versus Group C; these

comparisons being made within risk categories. This being the case, it is seen that the respective comparisons for DLC0 in IV drug users would be declared significant if the difference were greater than 0.8 and would be declared significant for the homosexual/bisexual comparisons if differences greater than 0.5 were observed.

Finally, Tables 3.7 through 3.10 show precision estimates for long-term mortality estimates and comparisons. In terms of Question 13, the comparison of interest is between the "intensively" screened and the "routinely" screened groups. For the overall long term mortality comparisons between the two groups, a mortality difference of 6% would be judged significant at the end of the study with this design.

Precision Estimates for
PCP Incidence Estimates and Comparisons*

Table 3.1

1/2 Confidence Intervals for Incidence

	A	B	C	Total
H/BS	0.02	0.04	0	0.02
IV	0.04	0.07	0	0.03
OTH	0.07	0.13	0	0.08
TOT	0.02	0.03	0	

Table 3.2

1/2 Confidence Intervals (Comparisons)

	AvsB	AvsC	BvsC
H/BS	0.05	0.02	0.04
IV	0.08	0.04	0.07
OTH	0.15
TOT	0.04	0.02	0.03

Table 3.3

1/2 Confidence Intervals (Comparisons)

	A	B	C	Total
H/BSvsIV	0.04	0.08	0	0.04
H/BSvsOTH	0.08	0.14	.	0.08
IVvsOTH	0.08	0.15	.	0.08

* Assumption for calculations were: After one year of follow-up,
Prevalence in A = 5%
Prevalence in B = 20%
Prevalence in C = 0%. (Source: Moss et al., Brit. Med. J., 1987; 1)

Precision Estimates for Comparison of DLCO
Among Disease and Transmission Groups****

Table 3.4

1/2 Confidence Intervals

	A	B	C	Total
H/BS	0.8	0.8	1.0	0.5
IV	1.0	1.0	1.8	0.8
OTH	2.0	2.0	...	1.5
TOT	0.5	0.5	1.0	

Table 3.5

1/2 Confidence Intervals (Comparisons)

	AvsB	AvsC	BvsC
H/BS	1.0	1.3	1.3
IV	1.5	2.0	2.0
OTH	3.0
TOT	0.8	1.0	1.0

Table 3.6

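### Question 2 groups subjects by whether PCP develops later in follow-up, which biases the hazard ratio for death downward and can make PCP appear protective

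*Protocol*

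**What the plan says.** Section 9 introduces Question 2 as the "association of various pulmonary diseases with subsequent morbidity and mortality". All seropositive subjects are analysed. The text says that "a Cox regression model will be used in which mortality is the dependent variable and the presence or absence of P. carinii pneumonia" is the predictor, and it defines the contrast as "adjusted survival rates for those patients who developed P. carinii pneumonia versus those who do not over the course of the study". The adjustment variables named there are transmission category, clinical and immunologic stage of HIV infection, and other coexisting diseases.

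Appendix 1, Question 2, repeats the question for PCP, tuberculosis, *M. avium* complex, cytomegalovirus and rarer diseases, with survival as one of six outcomes. Its list of confounders is longer and includes "Diseases developing subsequently".

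Section 7.1.3, item 8, excludes "Current or previous AIDS-defining diseases", but keeps a subject whose AIDS-defining disease is first found at the initial evaluation. PCP is on the AIDS-defining list in Appendix 10.

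Neither Section 9 nor Appendix 1 gives a time origin, a time-dependent covariate or a landmark for Question 2. Both kinds of safeguard appear elsewhere. Appendix 1, Question 8, says: "Regression models, appropriate when time dependant covariates are present, will be used to study this question". For Question 12, Section 9 sets the survival origin at randomization to avoid length-biased sampling.

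**The concern.** The question asks about mortality after PCP, but the stated contrast sorts subjects by something that happens during follow-up. A subject must live long enough to be diagnosed before counting as a PCP case. The time from entry to diagnosis is therefore free of deaths for that group, while everyone who dies before PCP could occur is counted in the other group. Both effects lower the apparent mortality of PCP.

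Course and outcome of the lung diseases belong to the primary objective (Section 2), and Section 9 names mortality as one of the primary outcome variables for this question. Followed as written, the analysis could report that PCP has little effect on survival, or even a favourable association, because of how follow-up time is allocated.

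**Working it through.** **Inputs.** One-year PCP rate 5% in Group A and 20% in Group B (Appendix 3, footnote to Tables 3.1 to 3.3). Three-year mortality 15% and 50% (footnote to the mortality tables). 527 subjects per group for analysis (Table 5B). Follow-up of 3 to 4 years (Section 5). First-episode PCP mortality of about 20% (Section 3.3), used in a sensitivity run. The true HR of death after PCP is not given; values from 1 to 6 are assumed.

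**The plan's own figures.** Question 2 has no stated precision, so the neighbouring figures built on the same inputs were reproduced.
- PCP incidence, A: 1.96 × √(0.05 × 0.95 / 527) = 1.86% (stated 2%).
- PCP incidence, B: 1.96 × √(0.20 × 0.80 / 527) = 3.42% (stated 3%).
- Mortality difference, with p = (0.15 + 0.50)/2 = 0.325: 1.96 × √(2 × 0.325 × 0.675 / 527) = 5.66% (stated 6%).

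All agree after rounding.

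**Hand check: Group B, three years, PCP with no effect on death.** Death hazard d = −ln(0.50)/3 = 0.2310 per year; PCP hazard l = −ln(0.80) = 0.2231; sum s = 0.4542. Per subject:
- PCP-free time: (1 − e^(−3s))/s = (1 − 0.2560)/0.4542 = 1.638 years.
- Deaths without PCP: 0.2310 × 1.638 = 0.3785.
- Total time: 0.50/0.2310 = 2.164 years, so time after PCP = 2.164 − 1.638 = 0.526.
- Deaths after PCP: 0.50 − 0.3785 = 0.1215.
- Time before diagnosis among those who get PCP: (l/s²) × [1 − e^(−3s)(1 + 3s)] = 0.427 years.

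With time split at diagnosis, the death rates are 0.1215/0.526 = 0.231 after PCP and 0.3785/1.638 = 0.231 before or without it, a ratio of 1. Grouped by ever/never, they are 0.1215/(0.427 + 0.526) = 0.127 and 0.3785/(1.638 − 0.427) = 0.313, a ratio of 0.41. The whole departure from 1 comes from moving 0.427 years of death-free time into the PCP group.

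**Simulation.** 1,054 seropositive subjects (527 A, 527 B), constant hazards, censoring uniform over 3 to 4 years, no loss to follow-up, 40 replicates. Baseline death hazards were recalibrated for each assumed HR so that three-year mortality stayed at 15% and 50%. Two Cox models were fitted, both adjusted for group: ever-PCP from entry, and PCP switched on at diagnosis.

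| Assumed true HR | Ever/never HR | Share of runs below 1 | Time-dependent HR |
|---|---|---|---|
| 1 | 0.39 | 1.00 | 0.98 |
| 1.5 | 0.57 | 1.00 | 1.48 |
| 2 | 0.73 | 0.98 | 2.01 |
| 2.5 | 0.89 | 0.82 | 2.56 |
| 3 | 1.04 | 0.40 | 3.00 |
| 4 | 1.34 | 0.00 | 4.02 |
| 6 | 1.89 | 0.00 | 6.03 |

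A second simulation with 60 replicates gave 0.40, 0.74 and 1.00 for true HRs of 1, 2 and 3.

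**With a 20% risk of death in the first month after PCP:**

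| Assumed HR after the acute phase | Ever/never HR | Time-dependent HR |
|---|---|---|
| 1 | 0.72 | 2.19 |
| 1.5 | 0.92 | 2.97 |
| 2 | 1.09 | 3.54 |
| 3 | 1.46 | 5.04 |

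In both tables the ever/never estimate is roughly 0.3 to 0.4 of the time-dependent one (from 1.46/5.04 = 0.29 to 0.39/0.98 = 0.40).

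**The case against.** **Is this detail left to an analysis plan?** Section 9 presents its worked questions as illustrations, Appendix 1 says it is not exhaustive, and Question 2 is framed as subsequent mortality. Covariate coding could properly be settled later. It is also true that the protocol never says PCP status is treated as known at entry or entered as a fixed covariate; a reader may infer that from the grouping, but it is not stated. What the protocol does state is the contrast itself, developed versus did not develop over the study. That is an ever/never comparison, and it is wrong for the question whatever coding is later chosen.

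**Does PCP come out protective?** Not necessarily. In the first table the estimate crosses 1 near a true HR of 3. With early PCP deaths added it crosses at a later-phase HR between 1.5 and 2. Above those points harm is understated, not reversed. The figure of 0.4 describes a PCP that causes no deaths, which Section 3.3 contradicts.

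**Do the models ignore residual confounding?** Yes. With an assumed log-normal frailty shared by PCP and death (20 runs each), true HRs of 1, 2 and 3 gave ever/never 0.48, 0.92 and 1.28 at SD 0.5, and 0.81, 1.27 and 1.74 at SD 1.0. The time-dependent model then overshot: 1.19, 2.50 and 3.85, and 2.04, 3.59 and 5.35. So time-dependent coding removes the immortal-time component only; stage and CD-4 must also be adjusted for. The ratio of the two estimates stayed between 0.33 (1.74/5.35) and 0.40 (0.48/1.19).

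**Wider readings that do not hold.** Question 1's model for "prevalence of P. carinii pneumonia at, for example, 2 years into the study, a logistic regression model will be utilized" might be taken for the same flaw. It does not compare survival by a future exposure, it is offered as an example, and Appendix 1 also plans incidence measures for that question. A reader might also infer that treatments enter as fixed covariates; the text lists them without saying how they are coded. Nor is the time-dependent wording in Question 8 confined to CD-4, since that question also lists antiviral and preventive therapy.

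**Conclusion.** The concern stands for Question 2. The stated ever/never comparison introduces immortal-time bias, because PCP is almost entirely a post-entry event and nothing written for this question corrects for it. The direction is downward throughout the range examined. On the plan's rates, true HRs of 1, 2, 3 and 6 appear as about 0.4, 0.7, 1.0 and 1.9; with 20% first-month mortality added, about 0.7 to 1.5 is reported where the time-dependent estimate is about 2.2 to 5.0. PCP can therefore look protective, but only for smaller true effects.

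These sizes rest on an assumed true HR, constant hazards, adjustment for group only, no loss to follow-up and no residual confounding. The few PCP cases found at the initial evaluation are not affected.

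The adjustment for later diseases is a lesser point. Such diseases may be consequences of PCP, so conditioning on them can remove part of the effect sought. A reader might infer that the mortality model already includes them, but that item is only in Appendix 1, which covers six outcomes; Section 9's list for the mortality model omits it. The two lists need to agree.

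**What to change.** In Section 9 and Appendix 1, Question 2:
1. Enter PCP, and each other Appendix 2 disease, as a time-dependent covariate: 0 before diagnosis and 1 from the diagnosis date. A case found at the initial evaluation is 1 from the start.
2. State the time origin.
3. Take stage and CD-4 from the last visit before diagnosis, so that the adjustment uses no value that the disease may already have changed.
4. Replace the ever/never survival comparison with curves from a landmark visit (grouped by status at that visit) or from diagnosis.
5. Remove the later-disease item from the mortality adjustment set in Appendix 1, in line with the Section 9 list.

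The cost is analysis wording. Table 6 already schedules CD-4 counts every 3 or 6 months, and the one-month mortality outcome in Question 12 already requires a PCP diagnosis date. For the other Appendix 2 diseases, it should be confirmed that the forms record a diagnosis date.
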